Objectives: The general objective of this study is to advance insight into non-pharmacological treatments for maturing women that impact psychological health and wellbeing of women adapting to menopause, a natural but often challenging developmental milestone. This exploratory study proposes to expand the knowledge in the menopausal literature and evaluate the effectiveness of CBGT in reducing problematic vasomotor symptoms, reducing daily interference and improving quality of life. The study will include two homogenous peri- or post-menopausal cohorts (African-American and Caucasian) with major depressive disorder or bipolar disorder. Anxiety disorders tend to be co-morbid with depressive disorders. Therefore, women with or without anxiety disorders will be included in this study.

The physiological mechanism that causes hot flashes is unknown but appears “to be associated with the rate of change of plasma oestrogen, which influences the thermoregulatory system via the hypothalamus” (Hunter & Smith, 2015, p. 5). The prevalence of hot flashes is thought to be associated with rapid estrogen withdrawal. The physiological mechanism for vasomotor symptoms is related to small fluctuations in core body temperature superimposed on an extremely narrow thermoneutral zone (TMZ). Hot flashes are triggered when the core body temperature rises above an upper threshold, causing sweating. When the core temperature decreases below the lower threshold of the TMZ, shivering occurs (Freedman 2005).

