The intervention will follow a manualized CBGT treatment developed by Hunter & Smith, 2015 aimed to reduce problematic vasomotor symptoms, stress, problems with sleep and enhance well-being. The CBGT will occur weekly for 6 weeks. Each week the CBGT is for 90 minutes. The underlying premise of CBGT is to promote stress coping and emotional regulation. This in turn will improve physiological regulation. For instance, improved stress coping decreases anxiety and allows women the opportunity to regulate their emotions and behaviors, potentially resulting in less physiologic lability. In addition, there is evidence to suggest that mood and stress and vasomotor symptoms are related to problems with memory and concentration. Problems with vasomotor symptoms, mood, memory and stress impact quality of life (Hunter & Smith, 2015). These symptoms will be assessed on the pre and post intervention. It is uncertain if the outcomes will be significant, which is why the research is being conducted. Since we are measuring each construct (i.e., hot flashes, daily life interference, quality of life), we will be able to test these theories.

Specific Aims and Exploratory Hypothesis

A manualized cognitive behavior group therapy treatment for vasomotor symptoms developed by Hunter and Smith (2105) has been found to significantly reduce hot flashes and night sweats for well women and women with breast cancer. The vasomotor symptoms of the participants were natural, surgically induced or followed medical procedures. Although not diagnosed with bipolar disorder, major depressive disorder or anxiety disorders, CBGT also reduced depressive and anxiety symptoms in these populations. However, the feasibility and effectiveness of this manualized treatment has not been studied for women who meet DSM-V criteria for bipolar disorder or major depressive disorder, with or without an anxiety disorder. In addition, no studies were found comparing Black and White females where group CBT was used as an intervention to reduce problematic vasomotor symptoms, quality of life and decrease daily interference.

Specific Aims:

1. Evaluate the feasibility of a manualized Cognitive behavior group therapy treatment for vasomotor symptoms for Black and White females diagnosed with bipolar disorder or major depressive disorder, with or without an anxiety disorder.

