2. Evaluate the effectiveness of a manualized Cognitive behavior group therapy treatment for vasomotor symptoms for Black and White females diagnosed with bipolar disorder or major depressive disorder, with or without an anxiety disorder.
3. Describe the characteristics for Black and White females diagnosed with bipolar disorder or major depressive disorder, with or without an anxiety disorder on the Hot Flush Frequency and Problem Rating Scale (HFFPRS), Hot Flash Daily Interference Scale (HFRDIS), Hot Flash Belief Scale (HFBS), Menopause Representation Questionnaire (MRQ), Montgomery Asberg Depression Rating Scale (MADRS), Perceived Stress Scale-10 (PSS-10), Snaith-Hamilton Pleasure Scale (SHAPS), Young Mania Rating Scale (YMRS), Structured Interview for the Hamilton Anxiety Rating Scale (SIGH-A) and the Short-Form Couple Conflicts (CTS2S).
4. Describe the following descriptive characteristics for Black and White females diagnosed with bipolar disorder or major depressive disorder, with or without an anxiety disorder: race/ethnicity, age, marital status, socioeconomic status, smoking status, average weekly alcohol and caffeine consumption, education, BMI, menopause status (early, late perimenopause, early, late post-menopause) and dosages and number of weeks on SSRI's, SNRI's, gabapentin or clonidine.

This study will also explore which independent variables are significant predictors of change in problematic hot flashes and night sweats, hot flash daily interference (HFRDIS), and menopause quality of life (MRQ) for peri- and post-menopausal Black and White females diagnosed with DSM-V bipolar disorder or major depressive disorder, with or without an anxiety disorder from baseline to post-treatment (6 weeks of Cognitive Behavioral Group Therapy). Examining which variables significantly contributes to the outcome variables will help direct non-pharmacologic treatment interventions and inform relevant psychoeducation for this population.

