It is expected that CBGT will reduce problematic hot flashes and night sweats (as measured via the hot flash frequency and problem rating scale), reduce daily interference (as measured on the hot flash daily interference scale), and improve quality of life (as measured on the MRQ). It is expected that strong negative beliefs about hot flashes and night sweats will be associated with more vasomotor symptoms and strong positive beliefs about vasomotor symptoms will be associated with significantly fewer vasomotor symptoms. The beliefs about vasomotor symptoms will be measured on the HFBS.

Overall Design: This is a 6-week cross-cultural study to test efficacy of CGBT treatment for 60 menopausal participants with major depressive disorder or bipolar disorder, with or without an anxiety disorder. The intervention will be delivered in groups of 5 to 10 participants per group of both race/ethnicities in an outpatient setting during a 6-week time period. The participants will be assessed on the degree of hot flash problem rating, hot flash related daily interference, and menopause quality of life at screening, baseline, and post-treatment. These are the outcome variables. Participants will be assessed using the following predictor variables at the same time points: BMI, level of perceived stress (PSS-10), severity of depression (MADRS), severity of

anxiety (SIGH-A), Snaith-Hamilton Pleasure Scale (SHAPS), Young Mania Rating Scale (YMRS), and hot flash beliefs. Severity of couple's conflict will be assessed using the CTS2S.

In addition, at the end of the study intervention, a questionnaire will be given to the participants to illicit feedback about the interventions. The purpose is to collect qualitative feedback that may be useful in future studies.

All participants will be seen for screening and treatment at University Hospitals Cleveland Medical Center, Mood Disorders Program [name].

Target Subject Population

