Concomitant medication(s): we will collect concomitant medication information on all medications a participant is taking at the time of screening and within the 90 days prior to screening. Participants will be asked if there have been any changes to medications at each study session.

Participant-rated

Quick Inventory of Depression Symptomatology-Self Report (QIDS-SR16): This 16-item scale will be used to measure depression severity. This self-reported questionnaire was developed based on the DSM-V diagnostic criteria for a major depressive disorder episode.

The Hot Flush Weekly Diary: This objectively measures the frequency and intensity of daily hot flashes and night sweats. It is used one week prior to starting the intervention to gather baseline data and then weekly during the CGBT sessions.

The Menopause Representation Questionnaire (MRQ): This is a 32-item scale developed by Hunter & O’Dea (2001) to assess the cognitive appraisal of menopause. The questionnaire was derived from self-regulation theory. The MRQ consists of 2 sections (identity and beliefs subscales). The identity scale measures symptoms that are attributed to menopause. The greater the symptom attribution to menopause the greater menopause was viewed as having a bigger impact on their life. The items on the identity scale are scored from 0-2, with *Yes= 2, Uncertain= 1 and No=0*. Summation of scores range from 0-40. The beliefs scales consists of 6 subscales, measuring positive and negative consequences of menopause, time frame and the coping/control scale, which measures feelings of control over menopause symptoms. The belief scale items are scored on a Likert scale- *Strongly Agree (5) to Strongly Disagree (1)*. Negative impact (1,4,6,10,12), relief/new phase (2,11,13) and control/coping (5,8,14,17) are used in the current study as they have higher reliability (personal communication with the author).

Hot Flush Frequency and Problem Rating Scale (HFFPRS): This is a 5-item rating scale assessing hot flush frequency and how much those hot flushes cause problems, distress or interferes with daily routine.

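### The third outcome is called quality of life, but the MRQ is described as measuring menopause appraisal, and no single MRQ score is named for analysis

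*Combined protocol and SAP*

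**What the plan says.** Quality of life runs through the design. Under Study Design & Objectives, the Objectives paragraph sets out to evaluate the therapy for "reducing problematic vasomotor symptoms, reducing daily interference and improving quality of life", and the description of the intervention lists quality of life among the constructs being measured. Specific Aims and Exploratory Hypothesis ties it to one instrument: the therapy is expected to reduce symptoms and interference "and improve quality of life (as measured on the MRQ"). Overall Design then lists the hot flash problem rating, daily interference and menopause quality of life as the outcome variables.

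The MRQ is described once, under Study Assessments (Participant-rated). Its purpose is "to assess the cognitive appraisal of menopause". On length: "This is a 32-item scale". It has an identity section, with items scored 0 to 2 ("Summation of scores range from 0-40"), and a beliefs section with six subscales, scored from 5 for strong agreement to 1 for strong disagreement. On use: "Negative impact (1,4,6,10,12), relief/new phase (2,11,13) and control/coping (5,8,14,17) are used in the current study", chosen for their higher reliability.

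Statistical Analysis plans matched-pairs t-tests on the outcome measures and regressions on the changes in three outcome variables, each at two-sided 0.05 without adjustment. Sample size determination sets alpha at 0.017 to allow for three outcomes. Neither section mentions an MRQ score.

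**The concern.** Two things do not fit together.

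- **Label and description.** The outcome is called quality of life, but the instrument paragraph never describes the MRQ as a quality-of-life measure. The therapy works on beliefs, so a shift in how women appraise menopause is a plausible result in its own right. Reported under the present label, that shift would be read as evidence for a different stated objective.
- **Count and scores.** The plan has one place for the MRQ among three outcomes, but the text yields three belief subscales, or four scores with the identity sum. A statistician working from the plan could not tell which number enters the t-test. The same gap affects the regression, including the race coefficient that the plan singles out. A plain sum is no way out: every belief item is scored upward with agreement, and by their names negative impact and relief/new phase point in opposite directions.

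**Working it through.** **1. The plan's own power figure.** Inputs from Sample size determination: 60 enrolled, 20% dropout, two-sided alpha 0.017, d = 0.5. I take d as standardised on the SD of the change.

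- Completers: 60 × 0.8 = 48.
- Alpha: 0.05 / 3 = 0.0167, which the plan rounds to 0.017.
- Paired t-test, noncentral t with 47 df and noncentrality 0.5 × √48 = 3.46: power 83.4%.
- At least 80% needs 45 completers; 45 / 0.8 = 56.25, so 57 enrolled.

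The claim of at least 80% power with 60 is reproduced.

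**2. MRQ scores in the text.**

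- Identity: a maximum of 40 at 2 points per item gives 40 / 2 = 20 items and one sum.
- Beliefs in use: 5 + 3 + 4 = 12 items in three subscales.
- 20 + 12 = 32, the stated length. This suggests that the identity section is collected, but it does not show that it is analysed, because the sentence on what is used names only the belief subscales. The match is not conclusive either: the listed item numbers run to 17, and 20 + 17 = 37.

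So there are three candidate scores, or four with identity.

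**3. Number of outcomes.** Take the problem rating and the daily interference scale as one score each.

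| MRQ scores tested | Outcomes |
|---|---|
| 1 | 2 + 1 = 3, as planned |
| 3 belief subscales | 2 + 3 = 5 |
| 3 belief subscales and identity | 2 + 4 = 6 |

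**4. Illustration of power.** Same test, 48 completers, d = 0.5:

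| Rule | Alpha per test | Power |
|---|---|---|
| Sample size section, 3 outcomes | 0.017 | 83.4% |
| Even split over 5 | 0.05 / 5 = 0.010 | 77.8% |
| Even split over 6 | 0.05 / 6 = 0.0083 | 75.7% |
| Statistical Analysis, unadjusted | 0.05 | 92.4% |

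The two middle rows apply only if the sponsor tests several MRQ scores and extends the split to all of them.

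**5. Label against description.** The closest the MRQ paragraph comes to quality of life is its remark that women who attribute more symptoms to menopause see it as having a larger impact on their lives. That is a perceived impact, so still an appraisal, and it concerns the identity section, which is not among the parts named as used.

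**The case against.** Several points on the other side carry weight.

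- **Perceived impact is close to quality of life.** The identity section is linked to impact on life, and one belief subscale is called negative impact. Whether an MRQ score can stand for quality of life may depend on the instrument's own literature, which is outside these documents. This stands in part: the documents show a mismatch between label and description, not that the label is wrong. The sponsor should be free to justify it.
- **Direction can largely be inferred.** The item scoring and subscale names make the favourable direction fairly clear for each score. This stands. The missing combination or reversal rule matters only if scores are pooled.
- **The study is exploratory.** The natural reading may be that all three subscales are analysed and reported, without adjustment. That excuses unadjusted testing, but not a count of three that the scores do not match, nor the label.

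A reader might go further and infer that the plan invites picking the best MRQ result after seeing the data. At 0.05, the best of three or four null scores would give a false positive with probability 1 − 0.95³ = 14.3% or 1 − 0.95⁴ = 18.5% under independence, or 12.5% or 15.6% at an assumed common correlation of 0.5. The plan proposes no such selection, so these figures describe what an unnamed score leaves open, not what is planned.

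A reader might also infer that the study is underpowered. The documents do not support that: the stated power is reproduced for three outcomes, and at the unadjusted 0.05 the power per test is 92.4% however many MRQ scores are tested.

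**Conclusion.** The concern holds as a question of definition and labelling. The third outcome is named as quality of life, its instrument is described as measuring appraisal, and the text gives three or four MRQ scores for one place in a count of three, with no total. Followed as written, a change in menopause appraisal would be reported as improved quality of life. There is no error in the sample size arithmetic. With one named score, power stays at 83.4% (48 completers, d = 0.5 on the change, alpha 0.017). The drop to 77.8% or 75.7% is conditional on testing five or six outcomes under an even split, which the plan does not state. This should be settled before analysis.

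**What to change.** - Name one MRQ score as the third outcome, with its direction of benefit, before analysis. The choice is the sponsor's.
- Report the other MRQ scores as exploratory.
- Label the result as menopause appraisal, or by the named subscale, wherever quality of life is stated as an objective, a measured construct or an outcome: the Objectives, the description of the intervention, Specific Aims and Exploratory Hypothesis, and Overall Design. The alternative is to document why the chosen score can be read as quality of life and keep the label.
- If several MRQ scores are to be tested, correct the count of three in Statistical Analysis and in Sample size determination, and restate alpha and power.
- Optionally, report item 10 of the daily interference scale descriptively. It asks about overall quality of life, but only as affected by hot flashes, and it is already part of the second outcome.

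With one named score, this needs wording only: no new data, visits or participants. The price is a narrower quality-of-life claim, unless the label is justified, and change on the remaining MRQ scores would count only as exploratory.

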Baseline: All participants will be asked to complete the following self-rated assessments: Hot Flush Frequency and Problem Rating Scale (HFFPRS), Hot Flash Belief Scale (HFBS), Menopause Representation Questionnaire (MRQ), Hot Flash Related Daily Interference Scale (HFRDIS), Snaith-Hamilton Pleasure Scale (SHAPS), Quick Inventory of Depression Symptomatology-Self Report (QIDS-SR16) and the Short-Form Couple Conflicts (CTS2S) scale within 2 days before or the day of the first group session. All participants will also be evaluated by clinician-rated assessments using the Montgomery Asberg Depression Rating Scale (MADRS), the Structured Interview for the Hamilton Anxiety Rating Scale (SIGH-A), the Young Mania Rating Scale (YMRS), and the Perceived Stress Scale-10 (PSS-10) within 2 days

before or the day of the first group session. All participants will be weighed at baseline. Baseline assessments can be done in person, via e-mail, or over the phone.

Study Interventions (week 0 through week 5):

Cognitive-Behavioral Group Therapy (CBGT)

The CBGT intervention will be delivered in groups of 5 to 10 participants including both African American and Caucasian females in an outpatient setting during a 6-week time period.

Treatment groups will start their first session when a minimum of 5 participants are conveniently enrolled, and each session will last for 1.5 hours. CBGT intervention will be facilitated by the primary investigator. The principal investigator will have periodic conference calls with Dr.

[name] to review the conduct of the group sessions and to discuss any concerns/questions.

[name] originally created the manual, and her role is serving as an advisor of this study.

Hunter & Smith's manual was developed from research studies on well-women and women with breast cancer (Alder et al., 2006; Mann et al., 2012). Permission has been given by [name] to use this manual in the proposed study. The six sessions are outlined in the manual entitled: *Managing Hot Flushes with Group Cognitive Behaviour Therapy: An Evidenced-Based Treatment Manual for Health Care Professionals* (Hunter & Smith, 2015) as follows:

Session 1: Psycho-education and the cognitive behavioural model

Session 2: Stress management, improving wellbeing and identifying precipitants

Session 3: Managing hot flushes using a cognitive behavioural approach

Session 4: Managing night sweats and improving sleep (part one)

Session 5: Managing night sweats and improving sleep (part two)

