
Session 6: Review and maintaining changes (One alteration: Open discussion about maintaining change in the context of other menopause-related issues or topics that were covered in sessions 1-5. Other related menopause issues may include topics such as weight changes, sexual functioning, and/or cognitive functioning. The group may discuss the challenges of maintaining change due to mood and/or anxiety disorders. The PI will facilitate this topic in lieu of maintaining change in the context of breast cancer. The group may chose topics for part of the final session as stated in the manual.

Study sessions will be audio recorded to assess reliability of following the treatment manual. The study sessions will be randomly reviewed by another study staff member to ensure quality control and fidelity will be verified by a checklist provided by [name].

End of Study (week 6): All participants will be asked to complete the same assessments completed at baseline. They will be asked to complete the following self-rated assessments: Hot Flush Frequency and Problem Rating Scale (HFFPRS), Hot Flash Belief Scale (HFBS), Menopause Representation Questionnaire (MRQ), Hot Flash Related Daily Interference Scale (HFRDIS), Snaith-Hamilton Pleasure Scale (SHAPS), Quick Inventory of Depression Symptomatology-Self Report (QIDS-SR16) and the Short-Form Couple Conflicts Scale (CTS2S). All participants will also be evaluated by clinician-rated assessments using the Montgomery Asberg Depression Rating Scale (MADRS), the Structured Interview for the Hamilton Anxiety Rating Scale (SIGH-A), the Young Mania Rating Scale (YMRS), and the Perceived Stress Scale-10 (PSS-10). All participants will be weighed at their end of study visit.

The data can be collected immediately after the end of the last study session or within 2 days of the last study session. End of Study assessments can be done in person, via e-mail, or over the phone.

The Hot Flush Weekly Diary will be collected each week.

Study Assessments

Demographics: including date of birth, race, ethnicity and smoking status

Medical and Treatment History: including date of last menstrual period, number of menstrual periods in the past year, and treatment received to treat vasomotor and/or mood symptoms.

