The Structured Interview for the Hamilton Anxiety Rating Scale (SIGH-A): This is a 14-item clinician-rated measure designed to assess the severity of anxiety.

Young Mania Rating Scale (YMRS): This is an 11-item clinician rated instrument designed to quantify severity of participant’s current symptoms of mania

BMI: A standard BMI calculator will be utilized for height and weight.

Table 1: Study Procedures Schedule

	Screening	TX(1) Baseline	TX(2)	TX(3)	TX(4)	TX(5)	TX(6) End of Intervention
Weeks		0	1	2	3	4	5
Visit	1	2	3	4	5	6	7
Intervention		X	X	X	X	X	X
Clinician Rated Assessments							
Demographics and Height	X						
Weight	X	X					X
Tracking and Documentation of Menstrual Cycles	X						
MINI	X						
MADRS	X	X					X
YMRS	X	X					X
SIGH-A	X	X					X
Concomitant Medications	X	X	X	X	X	X	X
Patient Rated Assessment							
QIDS	X	X	X	X	X	X	X

PSS	X	X					X
The Hot Flush Weekly Diary		X	X	X	X	X	X
HFFPRS		X					X
MRQ		X					X
HFBS		X					X
HFRDIS		X					X
SHAPS		X					X
CTS2S		X					X
Managing Menopausal Symptoms: Evaluation of Groups							X

Medication regimens to treat their DSM-V diagnoses will be encouraged to continue in order to determine if the CBGT accounted for any change in symptoms. Changes to medications during study participation will not be permitted. All concomitant medications taken during the study will be documented, including information on the indication, dosing, and dates of administration.

Efficacy & Data Analysis

Statistical Analysis:

Descriptive statistics will be used to describe demographic and clinical variables. This includes means and standard deviations for continuous variables and number and percentages for categorical variables. Difference in outcome measures from baseline to post-treatment will be determined by a matched-pairs *t*-test. Regression analysis will be used to assess the significance of the covariates on the differences of the 3 outcome variables. The significance of the race covariate in the regression models will be of special interest to the study. Statistical significance will be based on a Type I error rate of 0.05 for all statistical tests (two-tailed). Since this is an exploratory study no adjustment will be made for multiple comparisons.

Sample size determination.

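### The paired t-test treats women from the same therapy group as independent, and nothing planned would reveal within-group correlation (minor, low-cost improvement)

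*Combined protocol and SAP*

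**What the plan says.** **Delivery.** Overall Design: "The intervention will be delivered in groups of 5 to 10 participants per group of both race/ethnicities". The CBGT section adds: "Treatment groups will start their first session when a minimum of 5 participants are conveniently enrolled".

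**Analysis.** Statistical Analysis, under Efficacy & Data Analysis: "Difference in outcome measures from baseline to post-treatment will be determined by a matched-pairs" *t*-test. A regression then relates the change in the three outcomes to covariates, with race of special interest. Therapy group is not among the predictors or descriptive characteristics listed. The level is set in the same paragraph: "Statistical significance will be based on a Type I error rate of 0.05 for all statistical tests (two-tailed"), with no multiplicity adjustment.

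**Power.** Sample size determination uses a two-tailed level of 0.017, 20% dropout, 60 women and d = 0.5, and claims at least 80% power. It does not mention independence of participants.

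**Bearing on within-group correlation.** Session 6: "The group may chose topics for part of the final session as stated in the manual". End of Study: "The data can be collected immediately after the end of the last study session or within 2 days of the last study session". In the other direction: "CBGT intervention will be facilitated by the primary investigator", all groups follow one manual, and recorded sessions are "randomly reviewed by another study staff member to ensure quality control and fidelity".

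The supplied text contains no ICC, design effect, group term or sensitivity analysis for clustering.

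**The concern.** Women who share six sessions may change alike, because they share discussion, group mood and, in the last session, topics that the group chose itself. Outcomes may be collected straight after that session. If changes are positively correlated within groups, the mean change varies more than the paired *t*-test assumes. Its standard error is then too small, and it rejects too often when there is no true change.

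This test is the only pre-post test of effectiveness (Aim 2). What is at stake is how far a significant change can be relied on when later work is planned. As written, the analysis would give the reader no sign of whether clustering had mattered.

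**Working it through.** **Inputs.** From the documents: 60 women, 20% dropout, d = 0.5, levels 0.017 (sample size) and 0.05 (analysis), groups of 5 to 10. Assumed: equal groups, analysis of completers, and ICC from 0 to 0.10 for the change scores.

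**1. The plan's own figure.** Completers: 60 × 0.8 = 48. Under independence the noncentral *t* has 47 df and noncentrality 0.5 × √48 = 3.46. Power at 0.017 is 83.4%, so the claim of at least 80% reproduces. At 0.05 power is 92.4%.

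**2. Layouts.** 60/5 = 12 groups and 60/10 = 6 groups; 8 groups is an intermediate case. With 48 completers this gives m = 4, 6 or 8 per group.

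**3. Effect on the paired *t*-test.** Design effect DE = 1 + (m − 1) × ICC. The variance of the mean change is DE/48 in SD² units, while the sample variance has expectation (48 − DE)/47. The reported standard error divided by the true one is therefore about √{[(48 − DE)/47]/DE}.

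At ICC 0.05:

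| Groups × completers | DE | SE ratio | SE too small by |
|---|---|---|---|
| 12 × 4 | 1 + 3 × 0.05 = 1.15 | 0.931 | 7% |
| 8 × 6 | 1 + 5 × 0.05 = 1.25 | 0.892 | 11% |
| 6 × 8 | 1 + 7 × 0.05 = 1.35 | 0.857 | 14% |

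Multiplying the 5% critical value (2.012 on 47 df) by the ratio gives the effective cut-off. For 12 groups it is 2.012 × 0.931 = 1.87, a two-sided tail of 6.7%. For 6 groups it is 2.012 × 0.857 = 1.72, a tail of 9.1%. Simulation of the paired *t*-test agrees and gives:

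| ICC (assumed) | 12 groups | 8 groups | 6 groups |
|---|---|---|---|
| 0 | 5.0% | 5.0% | 5.0% |
| 0.02 | 5.7% | 6.2% | 6.6% |
| 0.05 | 6.7% | 7.9% | 9.1% |
| 0.10 | 8.5% | 10.9% | 13.2% |

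With no dropout (60 analysed, groups of 5 to 10) and ICC 0.05, the range is about 7.2% to 10.4%.

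**4. Does the planned test lose rejections?** Hardly. At d = 0.5, level 0.017 and ICC 0.05 it still rejects in 82%, 81% and 80% of simulated trials (12, 8, 6 groups). The harm is false positives.

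**5. The sensitivity analysis.** A *t*-test on group mean changes has (groups − 1) df and noncentrality 0.5 × √(48/DE). With equal groups it holds its nominal level at any ICC. At ICC 0 and level 0.017, with 11, 7 or 5 df, its power is 73%, 64% or 54%.

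Share of trials in which only the paired *t*-test is significant, at d = 0.5 and level 0.05 (simulation):

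| ICC | 12 groups | 8 groups | 6 groups |
|---|---|---|---|
| 0 | 5% | 9% | 15% |
| 0.05 | 8% | 15% | 23% |

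**The case against.** **The ICC is not in the documents and may be close to 0.** This stands. One facilitator, one manual, fidelity review and one site all limit differences between groups, and the written route to clustering is narrow: topic choice in part of one session. At ICC 0 the *t*-test is valid. What remains is that the plan has no means of showing which case applies.

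**The higher figures need large groups.** This also stands. Starting at five enrolled points to about 12 small groups, hence about 6.7% at ICC 0.05, an excess of 1.7 points. The 9.1% requires every group to enrol ten women. A reader might take 9.1% as the expected error rate; the documents do not support that.

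**The study is exploratory and single-arm.** Three unadjusted tests at 0.05 already allow up to 1 − 0.95³ = 14% familywise error if independent, and without a control arm a pre-post change cannot be attributed to CBGT. Both facts lower the stakes. Neither corrects a standard error that is too small, and the plan still applies a 0.05 rule.

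**The power statement.** A reader might infer that it is wrong or that 60 women are too few. It is neither: it reproduces for the test it describes. One could instead put the effective sample size (48/DE) into the power formula with 47 df and obtain 77%, 73% or 69% at ICC 0.05 and level 0.017. Those figures describe neither the planned *t*-test, which still rejects in 80% to 82%, nor a group-means test, which has far fewer df.

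**The race comparison.** A reader might extend the concern to the race coefficient. Groups contain both races, and in simulation at ICC 0.05 to 0.10 the ordinary regression test of race had a type I error of 4.1% to 5.1%, so this point does not reach it.

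**The identifier may already exist.** Session records probably allow group membership to be recovered, and the confidentiality text refers to a data-collection section that is not in the supplied document. That the field is missing cannot be asserted.

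**Conclusion.** The point holds as a minor, low-cost improvement. It is certain from the text that treatment is given in groups, that the effectiveness test ignores the groups, and that no planned analysis would reveal within-group correlation. The size is uncertain because it depends wholly on an assumed ICC: no inflation at 0, under 2 points at 0.02, and about 2 to 4 points at 0.05, with the smaller figures more likely under the start-at-five rule. These results also assume 48 completers in equal groups.

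The conclusion is confined to the pre-post *p*-value, its standard error and the unstated condition behind the power figure. It does not make the paired *t*-test invalid or the sample size wrong, and it is not a design failure.

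**What to change.** 1. **Data.** Make sure the analysis dataset holds a therapy-group identifier for each participant.
2. **Analysis.** Keep the paired *t*-test as the main analysis. For each of the three outcomes, pre-specify one sensitivity analysis: a *t*-test on therapy-group mean changes with (groups − 1) df. If completer numbers differ clearly between groups, use weights or a random group effect with Kenward-Roger df instead; fix in advance what counts as clearly unequal and which alternative applies. Report the estimate and confidence interval, and describe a result that is significant only in the paired *t*-test as sensitive to clustering.
3. **Sample size text.** State that the 80% power is for the paired *t*-test and assumes independent participants. Do not present effective-sample-size calculations on 47 df as the power of the group-aware analysis.

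**Cost.** One data field and a few sentences; no extra patients or visits. The real price is a wide interval from few groups. Even with no clustering, a true effect of d = 0.5 would be labelled sensitive to clustering in about 5% of trials with 12 groups and 15% with 6. The text should say that this label may reflect the small number of groups and is not evidence of clustering in itself. That is also why the group-means test should sit beside the planned test and not replace it.
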